- 1) *All-trans retinoic acid is a potent inhibitor of CYP7A1 in isolated human and rodent hepatocytes and reduces the bile acid pool size by 50% in bile duct ligated rat model of cholestasis resulting in significant reductions in liver injury (4-5).*
- 2) *Studies with ATRA administration to patients with PSC confirm that ATRA inhibits CYP7A1 (6).* This was observed through a Human Pilot studying the combination of ATRA and UDCA conducted at Yale and Mayo Clinics (HIC 1012007734). However, the full dose of ATRA, which is already in clinical use and FDA approved for management of acute promyelocytic leukemia, resulted in frequent side effects such as self-limited headaches and this indicates the need to evaluate efficacy of ATRA in patients with PSC while using lower doses.

Bibliography

1. *Allen et al. AJP 178:175, 2011.*
2. *Cai SY et al. Hepatology 60:300A, 2014.*
3. *Cai SY et al. 62:610A, 2015.*
4. *Cai SY et al. J.Lipid Res 51:2265, 2010.*
5. *He et al. Hepatology 53:548, 2011.*
6. *Assis DN et al. J Clin Gastroenterol. 51: e11-e16, 2017.*

4. Research Plan: Summarize the study design and research procedures using non-technical language that can be readily understood by someone outside the discipline. Be sure to distinguish between standard of care vs. research procedures when applicable, and include any flowcharts of visits specifying their individual times and lengths. Describe the setting in which the research will take place.

We propose an investigator-initiated efficacy trial of low dose ATRA monotherapy in a small group of patients with PSC to be conducted at the Yale Liver Clinics.

Study Design for an efficacy trial of low dose All-Trans Retinoic Acid (ATRA) in Primary Sclerosing Cholangitis (PSC)

- I. Objective: Evaluate effects of low dose ATRA therapy on serum alkaline phosphatase (ALP) over 24 weeks in adults with PSC.
- II. Study Design: Single-arm, open label study in PSC, comparing pre-treatment and post-treatment serum ALP levels in individual subjects and as a group.
- III. Number of Subjects: Goal of enrolling 20 adult subjects with PSC.
- IV. Dosage and Administration: ATRA 10 mg tablets will be taken with food once daily for 3 days and then increase to twice daily for the remainder of the study. With an option to dose escalate to 20 mg twice daily if Alk Phos does not reduce 5% or more after the first 12 weeks.
- V. Efficacy Evaluation
 - Primary Endpoint: Percent change of serum ALP from baseline to week 24

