 - Other Endpoints: The percent of patient who have the following from baseline to weeks 12 and 24, normalization of ALP, ALP < 1.5 x ULN and 50% reduction, reduction in C4, serum bile acids, ALT and serum ELF score improvement in fibrosis per Transient Elastography by at least 1 stage .
- VI. Safety Evaluation
 - Evaluate safety of ATRA with respect to frequency and severity of adverse events.
- VII. Facilities and Equipment
 - ATRA will be stored and dispensed for the study through the Yale New Haven Hospital Research Pharmacy.
 - Enrollment for the study will occur at the Yale Liver Center Clinics, [name] as well as the Yale Church Street Research Unit the CSRU.
 - Study visits will occur at the Yale Liver Center Clinics, [name] as well as the Yale Church Street Research Unit the CSRU.
 - Blood samples and research analyses will be stored and tested at the Yale Liver Center research building (TAC).
 - Clinical labs will be performed as per standard lab testing at the Yale New Haven laboratories.
- VIII. Screening Treatment and Follow up Visits

All below procedures are research related not standard of care.

 - Screening will be within 6 weeks of the Baseline Visit.
 - Subjects will be seen in clinic for screening, on treatment weeks 1, 4 and 12, end of treatment week 24, and follow up week 28.
 - Phone calls will be made to the patient on weeks 8 and 16.
 - If after week 12 the Alk Phos has not reduced 5% or more the dose will be doubled, and the wk 16 phone call will be replaced with an additional clinic visit.

- Approximately 60 mL or 4 tablespoons of blood will be drawn at each of the above clinic visits and again at week 48.
- Clinical Lab Testing: Serum ALP, total/direct bilirubin, AST, ALT, GGT, albumin, serum bile acids, lipid panel, basic metabolic panel, CBC, PT/INR.
- Research Lab Testing: Serum C4, MCP-1, IL-8, serum ELF.
- Additionally, blood will be stored in a de-identified way in order to perform potential genetic and other tests to understand the risks factors for the development of PSC.
- Imaging: Transient Elastography (Fibroscan) at Baseline Visit, and week 24.
- Complete and symptom based physical examinations and quality of life questionnaires will be performed at each visit.
- Symptoms will also be assessed by phone at weeks 8 and 16.

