- If at any point the Bilirubin, Alk Phos, AST or ALT increases 1.5 x over the patients baseline value, the ATRA will be held for 2 weeks. After 2 weeks the labs will be retested, and if the value is under 1.5 x the patients baseline value ATRA will be restarted at the same dose. If the value remains over 1.5 x the patients baseline value after 2 weeks the patient will be discontinued from the study treatment.

The screening and end of treatment visit (week 24) will take about 30-40 minutes, the on treatment visits (weeks 1, 4 , 12) and follow up 1 (week 28) will take about 20-30 minutes, follow up 2 (week 48) will take about 10 minutes, and the phone calls on week 8 and 16 will take about 10 minutes.

Women of childbearing age will need to use two forms of contraception, and have a negative pregnancy tests at screening and every study visit. A total of 6 pregnancy tests will be taken which will be paid for and provided by the research study.

5. Genetic Testing N/A

A. Describe

- i. the types of future research to be conducted using the materials, specifying if immortalization of cell lines, whole exome or genome sequencing, genome wide association studies, or animal studies are planned There is the potential for the banked specimens to be used for immortalization of cell lines, whole exome or genome sequencing, genome wide association studies, and animal studies.
- ii. the plan for the collection of material or the conditions under which material will be received blood samples will be collected by a trained phlebotomist.
- iii. the types of information about the donor/individual contributors that will be entered into a database We will use oncore.ynhh.org for the patient's information. Oncore will hold all of the current study data, and if samples are stored for future use. We will also use Epic for appropriate documentation.
- iv. the methods to uphold confidentiality The study personal will use oncore with encrypted laptops or university computers.

B. What are the conditions or procedures for sharing of materials and/or distributing for future research projects? The genetic material collected from the blood samples for future research projects may be shared within the network of physicians who have a professional working relationship with the PI and SubIs.

C. Is widespread sharing of materials planned? No

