- History of cancer in the preceding 5 years, except adequately treated non-melanoma skin cancer, carcinoma in situ of the cervix, in situ prostate cancer.
- Viral hepatitis including hepatitis A, B, C, D, E.
- Decompensated cirrhosis, or planned liver transplantation.
- Recent diagnostic or therapeutic biliary manipulation (endoscopic, radiologic) within the past 3 months.
- Ascending Cholangitis requiring antibiotics within the past 3 months.
- Uncontrolled IBD, or IBD requiring the use of steroids.
- Acute or Chronic Kidney Disease with serum creatinine > 2 mg/dL.
- Allergy to ATRA or vitamin A compounds.

9. How will eligibility be determined, and by whom? Write here

The principal investigators, sub-investigators and/or delegates under their direct supervision will determine eligibility in accordance with the requirements of the protocol.

10. Risks: Describe the reasonably foreseeable risks, including risks to subject privacy, discomforts, or inconveniences associated with subjects participating in the research.

The medication ATRA has been associated with possible side effects in patients who have leukemia and who take the drug orally for that disease. These side effects include:

- Chest discomfort – up to 32% of patients.
- Abnormal heart rhythms – up to 23% of patients.

Both chest discomfort and abnormal heart rhythms are adverse reaction listed for tretinoin (a related form of ATRA). The symptoms will be monitored by the treating physician by asking the patient if they are having chest discomfort or irregular heartbeats. Additional protocol specific monitoring should not be needed, however if a patient is experiencing symptoms an evaluation including an EKG will be pursued and the appropriate CTCAE term and grade will be documented in the patient's chart.

- Increased triglyceride levels – up to 60% of patients.
- Dry skin – up to 77% of patients.
- Nausea – up to 57% of patients.
- Weight gain – up to 23% of patients.
- Retinoic Acid Syndrome – a specific series of symptoms in patients with leukemia who are taking ATRA, in up to 75% of patients taking the drug for that specific disease. Symptoms include fever, shortness of breath, weight gain, increased white blood cell count, and fluid accumulation around the lungs and heart. This typically occurs within the first month of treatment.
- Liver Test Increase – a mild increase in liver tests has been found in up to 60% of patients taking ATRA for leukemia.
- Dizziness – up to 20% of patients.

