- Headache – up to 86% of patients.
- Infections – up to 58% of patients.
- Risk of fetal malformations – ATRA is a pregnancy category D medication. There is a high risk of birth defects in babies born to mothers taking ATRA. Therefore, ATRA should not be used during pregnancy. If ATRA is used by a child-bearing aged mother, a negative pregnancy tests should be performed before taking the drug. A pregnancy test should also be done at every study visit. Two forms of contraception should be used while taking the drug, and for the month following discontinuation of the drug. Pregnancy should not be planned for up to 6 months after stopping the medication. Treatment should be stopped immediately if pregnancy develops.

Other than the pregnancy risks described above, it is not known if these side effects are seen as often or at all in patients who do not have leukemia and who have liver conditions such as PSC.

For those who develop headaches from ATRA, this symptom goes away within a few days for the majority of patients. If the subject experience a significant headache or similar symptom, but are otherwise healthy and still able to participate, we will reduce the dose of your medication so that you can tolerate the medication more easily.

In our previous Pilot of ATRA and UDCA in PSC the following frequency of adverse effects was observed as reported below (6). None were grade 3 or above:

TABLE 2. Reported Adverse Effects

Adverse Effects	Frequency (%)
Headache	63
Tinnitus	26
Diarrhea	16
Dry skin/mucus membranes	10
Myalgia	5
Anemia	5

Privacy risks are always a potential risk of a clinical study, but will be minimized by stringent procedures to ensure compliance with local and federal regulations regarding protected health information. We do not believe that this study poses an elevated risk for breach of subject privacy.

We do not believe subjects participating in the study will suffer from significant inconveniences, since they are currently under treatment by physicians at Yale, and thus are presenting to their usual centers of care, at which the study will be conducted.

11. Minimizing Risks: Describe the manner in which the above-mentioned risks will be minimized.

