For more guidance on Adverse Event reporting and DSMPs, see IRB Policy 710 Reporting Unanticipated Problems Involving Risks to Subjects or Others, including Adverse Events

13. Statistical Considerations: Describe the statistical analyses that support the study design.

This is an exploratory Efficacy and Safety Human Pilot to determine if low dose ATRA is effective for reduction of cholestasis in patients with PSC and with a more favorable side effect profile with dose reduction. Although low dose ATRA monotherapy has not yet been studied in patients with PSC, we hypothesize a 30-40% reduction in serum Alkaline Phosphatase from baseline to week 24, which would require approximately 20 patients to achieve 90% power to detect a this difference at alpha of 0.05 using a two-sided one-sample t-test.

SECTION II: RESEARCH INVOLVING DRUGS, BIOLOGICS, RADIOTRACERS, PLACEBOS AND DEVICES

If this section (or one of its parts, A or B) is not applicable, check off N/A and delete the rest of the section.

A. RADIOTRACERS N/A

1. Name of the radiotracer: *Write here*
2. Is the radiotracer FDA approved? YES NO

If NO, an FDA issued IND is required for the investigational use unless RDRC assumes oversight.

3. Check one: IND# *Write here* or RDRC oversight (RDRC approval will be required prior to use)

B. DRUGS/BIOLOGICS N/A

1. If an exemption from IND filing requirements is sought for a clinical investigation of a drug product that is lawfully marketed in the United States, review the following categories and complete the category that applies (*and delete the inapplicable categories*):

Exempt Category 1: The clinical investigation of a drug product that is lawfully marketed in the United States can be exempt from IND regulations if all of the following are yes:

1. The intention of the investigation is NOT to report to the FDA as a well-controlled study in support of a new indication for use or to be used to support any other significant change in the labeling for the drug.	
2. The drug that is undergoing investigation is lawfully marketed as a prescription drug product, and the intention of the investigation is NOT to support a significant change in the advertising for the product.	

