Despite being generally well tolerated in clinical practice for patients with leukemia, there are several potential toxic effects of oral ATRA including hyperlipidemia, exacerbation of coronary artery disease and arrhythmias, teratogenicity (pregnancy category D), hyperleukocytosis (in leukemic patients), and increased liver function tests (3). A unique adverse event from ATRA in APL involves retinoic acid syndrome, caused by capillary leak from leukemic cells and can be induced by ATRA (7). This does not appear to be a potential toxic effect in patients without APL. In routine clinical practice hepatotoxicity while on ATRA is uncommon, though if this develops it appears to have a similar profile to that of vitamin A toxicity, and resolves with discontinuation of the drug (3,8). One case report describes severe hepatotoxicity attributed to ATRA in a patient receiving the drug for APL (9).

There is little published data on the use of oral ATRA for patients with liver disease. The study by Bocher *et al.* (5) from 2008 evaluated oral ATRA (dosed at 45 mg/m² per APL treatment recommendations) for 90 days in patients with hepatitis from chronic hepatitis C virus infection. Subjects in this study did not demonstrate elevations in their aminotransferase levels or develop other evidence of hepatotoxicity (or other serious adverse effects). In fact, levels of AST and ALT diminished in all patients. Based on this literature data, and the encouraging results of pre-clinical studies, initial human with oral ATRA for 90 days was justified for purposes of a feasibility pilot study for patients with PSC. Since there is no clear data in humans to guide in the dosing of ATRA in cholestatic liver disease, this initial pilot used the FDA-approved daily oral dose of 45 mg/m² (2). The efficacy of ATRA and UDCA combination therapy is shown below regarding changes in alkaline phosphatase, AST, ALT, and reduction of bile acid intermediate C4.

The recorded adverse effect frequencies in the combination study pilot are shown below.

TABLE 2. Reported Adverse Effects

Adverse Effects	Frequency (%)
Headache	63
Tinnitus	26
Diarrhea	16
Dry skin/mucus membranes	10
Myalgia	5
Anemia	5

c. Marketing Experience

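### Does the plan leave patients stopped for a lasting ALP rise out of the primary week-24 test?

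*Combined protocol and SAP*

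**What the plan says.** Section I, item 4, part V gives "Primary Endpoint: Percent change of serum ALP from baseline to week 24". Part III sets the size: "Goal of enrolling 20 adult subjects with PSC".

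Part VIII holds ATRA for two weeks if bilirubin, ALP, AST or ALT rises 1.5 times over the patient's baseline, then adds: "If the value remains over 1.5 x the patients baseline value after 2 weeks the patient will be discontinued from the study treatment". The same part gives one schedule for everyone: "Subjects will be seen in clinic for screening, on treatment weeks 1, 4 and 12, end of treatment week 24", then a follow-up visit at week 28. Blood is drawn at each clinic visit and again at week 48. No separate schedule exists for patients who stop early.

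Section I, item 5.E says that no further samples are taken once a subject withdraws from the study. It does not mention patients who only stop treatment.

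Section I, item 13 is one paragraph. It hypothesises a 30-40% fall in ALP and says this "would require approximately 20 patients to achieve 90% power to detect a this difference at alpha of 0.05 using a two-sided one-sample t-test". It gives no SD, analysis set, missing-data rule or dropout allowance.

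**The concern.** One of the variables that can end treatment is also the primary endpoint. A patient stopped for ALP was more than 50% above baseline at the retest, after two weeks off drug. If such patients were left out of the t-test, the loss would depend on the outcome and would usually move the mean toward benefit. A single-arm trial has no control group in which the same loss would show. A week-24 sample that was never drawn cannot be recovered at analysis.

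The label for week 24 adds to the worry. It is called the end-of-treatment visit, and a reader might take that to exclude someone whose treatment ended at week 6. The enrolment goal also equals the number in the power statement, which leaves no visible allowance for losses.

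The documents do not say how often the rule would fire. Section I, item 10 says of ATRA that "a mild increase in liver tests has been found in up to 60% of patients taking ATRA for leukemia", and also that "it is not known if these side effects are seen as often or at all in patients who do not have leukemia". Section II, Effects in Humans, states: "In routine clinical practice hepatotoxicity while on ATRA is uncommon".

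**Working it through.** **1. What the text implies for a stopped patient.**
- The rule in item 4, part VIII ends study treatment. It does not end participation.
- The schedule in the same part applies to all subjects, with a clinic visit and blood draw at week 24.
- Item 5.E ends sampling on withdrawal from the study, which is a different event.
- Item 13 applies the test to the change from baseline to week 24 and sets no condition on being on treatment.

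Together these give a default: the patient stays in follow-up, has ALP drawn at week 24 and enters the test. No sentence says otherwise.

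**2. The plan's own figure.** For a two-sided one-sample t-test at alpha 0.05 (exact noncentral t, 19 degrees of freedom), 90% power with n = 20 needs a standardised effect of 0.7645. The implied SD of percent change is 30 / 0.7645 = 39.2 points for a 30% fall, or 40 / 0.7645 = 52.3 for a 40% fall. No SD is given, so 20 can be neither confirmed nor refuted. If 20 is exactly what is needed, analysing 19, 18, 17 or 16 patients gives power of 88%, 86%, 84% or 82%. If the SD is 30, a 30% fall with 16 analysed still has 96%.

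**3. Arithmetic if a stopped patient were left out.** Suppose the others average -30% and k of the 20 have week-24 change v. The mean over all 20 is ((20 - k)(-30) + kv) / 20, so leaving the k out overstates the fall by k(30 + v) / 20. For k = 1:
- v = 0 (ALP back at baseline): 30/20 = 1.5 points
- v = +25: 55/20 = 2.75 points
- v = +50: 80/20 = 4 points

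**4. Illustrative model, again only if they were left out.** Assumptions: 20 patients; normal percent change with the same mean at every visit; correlation 0.5 to 0.8 between any two measurements; a patient is left out if above +50% at week 1, 4 or 12 and again on retest. Ranges run over the correlation.

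| True mean change | Result | SD 25 | SD 30 | SD 39.2 |
|---|---|---|---|---|
| 0 | Shift toward benefit, points | 0.4-1.0 | 1.2-2.4 | 3.6-6.3 |
| 0 | False-positive rate for benefit (2.5% if all are counted) | 2.9-3.4% | 3.6-4.9% | 5.7-9.6% |
| -15% | Shift, points | 0.1-0.2 | 0.3-0.8 | 1.6-3.2 |
| -30% | Shift, points | 0.0 | 0.1-0.2 | 0.6-1.4 |
| -30% | Chance that anyone is left out | 0.2-0.7% | 2-5% | 17-29% |

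The model omits the extra week-16 visit for patients whose ALP has not fallen by 5% at week 12, and it assumes the full drug effect from week 1. Relaxing either assumption makes the bias larger, so the table illustrates the size and does not bound it.

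**The case for a change.** The strongest case for a change is that an implied default is weaker than a stated one. Low-dose monotherapy has not been studied in PSC, so little or no effect is a real possibility, and that is where leaving patients out does most harm. With 20 patients, one omission can move the mean by several points. A sentence confirming the draw would cost almost nothing, because week 24 is already a scheduled visit.

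Much of this stands. The plan is silent on the analysis set, the direction of the bias is right for ALP-triggered stops, and the arithmetic reproduces. Three things limit it.

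First, the harm requires someone to act against the natural reading of the schedule. An added sentence would mostly write down what the text already implies, and it would not settle what to do when a week-24 ALP is still missing, for example after withdrawal of consent.

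Second, the large figures need several conditions at once: exclusion of stopped patients, no drug effect, and an SD near 39 that is only back-solved from the sample size. Stops for bilirubin, AST or ALT alone have no certain direction.

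Third, the evidence in the documents closest to this population does not point to frequent stops. The adverse-effect table of the PSC pilot, at the full ATRA dose with UDCA, lists no liver-test rise, and no event was grade 3 or above. In the hepatitis C study described in Section II, AST and ALT fell in all patients. Neither excludes an ALP rise from PSC itself.

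Stating that the power assumes 20 evaluable patients would correct no figure either: without an SD, the 90% cannot be shown to be missed.

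**Conclusion.** No change follows. The plan does not spell out that patients taken off ATRA keep their week-24 draw and enter the primary test, but the common visit schedule and a rule that ends treatment only lead there. This is a gap that analysts fill sensibly in an exploratory 20-patient pilot. The protocol also plans to compare ALP in individual subjects as well as for the group, so stopped patients could be seen one by one.

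The size, should they be left out after all, rests on an SD and correlation that the documents do not give. In the model it ranges from nil to about 1.4 points at the hypothesised 30% fall. With no effect and an SD of 39.2 it reaches 3.6 to 6.3 points, with a false-positive rate for benefit of up to 9.6%. The conclusion would be different if the text tied the week-24 draw or the primary test to still being on treatment; it does neither.
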